- 1. reductions in weekly FI episodes (primary outcome) and,
- 2. improvements in validated incontinence scores, patient-centred FI-related symptoms and disease-specific and generic quality of life measures (secondary outcomes);

Design

[figure not shown]
The proposed study is a UK based multi-centre (at least 14 centres) double-blinded, placebo-controlled trial of 212 participants randomised to receive the intervention (PTNS) or sham (needle insertion and TENS): 106 in each arm. All participants follow an assessment period, recruitment, allocation, standard 3 month treatment protocol (one 30 min session per week) with primary outcome determined at 14 weeks on an intention to treat basis.

The following pragmatic considerations were included in study design:

- 1. All participants randomised who receive the first treatment will be included in the intention-to-treat analysis of primary endpoint. Those in whom post-treatment data are unavailable at 14 weeks for any reason (loss to follow up, failure to complete treatment) will have their outcomes defined using the interim bowel diary data collected between treatments 6 and 7 (Visits 7 and 8). Those who do not have this data available (again due to loss to follow up or failure to complete treatment) will be defined as non-responders and their 14 week outcome imputed from their baseline FI frequency. Prior to the first treatment, it is anticipated that some participants (up to 10%) will fail to attend after eligibility is assessed due to a failure of compliance with the travel and attendance needs of the treatment course or study. These will not count as study recruits. Based on our own department's data and supported by the study of Peters et al., [41] it is anticipated that the dropout rate after the first intervention is complete will be 6%. This level is acceptable to analyse secondary endpoints using available case analysis. The reason for this interim bowel diary assessment is two-fold;
 - a. to gauge response to a short course of treatment (since some people believe a 12 week course is not necessary);
 - to allow us to collect 'real' data regarding those participants who do not complete the full 12 week course of treatment, in an attempt to judge whether this was due to objective lack of response.

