
These will be assessed using bowel diaries and investigator-administered questionnaires. Bowel diary data will be collected at week -2 to 0 where 0 is start of treatment and -2 is baseline pre-randomisation, and at 14 weeks for the 2 preceding weeks post intervention i.e. weeks 12-14. There will also be a 1 week bowel diary collected between Visits 7 and 8, half way through the treatment duration. This is when participants usually start to perceive benefit. This will help to improve the quality of data on participants who withdraw from the study as outcomes will be analysed using the last available data on those participants who do not complete the final 2 week bowel diary. In those patients who withdraw from the study prior to completing the final study visit no secondary outcome data will be available for analysis. The bowel diaries will record number and type of incontinence episodes per week (and associated symptoms). An episode of faecal incontinence is defined as 'any episode considered significant enough by the participant to include on their bowel diary'.

Primary:

Responder vs. non-responder: Defined as a 50% or greater reduction in FI episodes per week (on intention-to-treat).

Secondary:

- a. Percentage reduction in FI episodes per week in addition to informing the primary outcome, this will give a confidence interval of effect and permit calculation of the proportions of patients who achieve complete continence or no change / deterioration (used in one Cochrane review of surgery for FI: [53]).
- b. Mean reduction in FI episodes per week. The confidence interval of this measure will be important for clinical interpretation of effect.
- c. Validated and reliable patient-rated quantitative outcomes including symptom severity scores (Cleveland Clinic Score) [50], validated disease-specific: FI-QOL [24] and generic: EQ-5D [54] quality of life measures will be employed.

- d. Recently-described patient-centred qualitative outcome tools have identified 5 key issues [8]. These will be employed as suggested by NICE (2007) research recommendations [32] and are anticipated to provide more clinically meaningful outcomes.
- e. Likert scales of patients global impression of success (0-10). These have been employed infrequently in the FI literature but will help to validate the primary outcome (a).
- f. Short urinary symptom assessment. As many patients have combined FI and urinary incontinence symptoms it will be of value to assess both.

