The SAE will be recorded in the participants' CRF folder and the participant followed up with regular phone calls and at the following appointment the following week. The SAE form is scanned and emailed or faxed to the sponsor. The email address the form should be sent to at the Joint R&D Office (JRO) is: [contact]

The fax number is: [name]

There are no SAEs expected to occur in this population. Therefore, all related SAE's are reportable as outlined above.

Withdrawal Criteria

Participants will be withdrawn from the trial if they fulfil any of the criteria below at any point following delivery of the first treatment.

- Participant no-longer wishes to be involved in trial
- Participant develops medical condition which fulfils part of the exclusion criteria
- Participant becomes pregnant
- If, for any reason, the participant has to be unblinded
- Participant lost to follow up (could not be contacted by telephone or other means)
- Intercurrent illness
- Death

When a participant is withdrawn from the study, the Early Withdrawal from Study CRF will be filled in by a researcher. In order to ensure clarity of each participants outcome, the researcher should also complete the final study visit (CRF 7).

Once a participant has withdrawn from the trial, they will be followed up on the NHS in the usual way, and progress down the usual treatment protocol.

Proposed sample size

Previous publications [36-39] and our own data [40] on 50 patients suggest a 60% success rate for PTNS on the basis of above justified primary outcome measure. There are no RCT data for PTNS in FI. However the pivotal level I SumiT trial of PTNS in overactive bladder symptoms (OAB) [41] which used a similar global response assessment of urinary incontinence and intention to treat design, observed a moderate or marked improvement in symptoms in 55% PTNS group and only 21% sham group. On the basis that placebo responses are frequently higher for bowel rather than bladder symptoms [43-45] we have selected a sham response rate of 35% whilst keeping this more conservative estimate of treatment response of 55%. We believe this difference remains clinically important in relation to other therapies such as SNS. 212 participants are required to detect this difference with 80% power at the 5%

significance level. We will recruit 235 participants at baseline to allow for a 10% failure to attend the 2nd visit (allocation and first intervention).

Feasibility

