Outcomes will take the form of binary (success or failure: primary outcome measure), count (change in number of FI episodes), ordinal (patient's global impression of success) and continuous (GIQOL, SF36, FI score, and EQ-5D) data. Regression models, with a fixed effect for centre, appropriate to the outcome data types will be fitted to estimate the treatment effect, adjusting for baseline values (when appropriate), sex, and loperamide use/fibre supplements as potential confounders (the dose and frequency of these will be recorded at all visits). Analysis will be performed using proprietary software (Stata version 10.1, Stata Corp. Texas) by the PCTU study statistician ([name]). P < 0.05 will be taken to indicate statistical significance. Given the stability of FI over a short period of time, where follow-up scores are missing, these will be imputed using the baseline scores, or interim bowel diary scores if available. The rationale for this is that primary outcome would, in the absence of any intervention, be expected to remain stable over the relatively short time span of the trial. Any changes or deviations from the original statistical plan will be described and justified in the Clinical Study report. Every attempt will be made to avoid any deviations from the original statistical plan.

Ethical approval

PTNS is CE-marked and clinically established in the NHS. A favourable ethical opinion has been given (ELCHA REC 10/H0703/25 June 2010); Amendment 1 approved 19th Oct 2010 and Amendment 2 approved 6th June 2011.

PTNS treatment and placebo have no recognised significant adverse effects. Although the trial necessarily delays 'real' treatment of participants in the sham arm, this time has been limited to just over 3 months (discussed with [name], Prof of Bioethics and Law, QMUL). PTNS or an alternative treatment e.g. SNS can be offered immediately thereafter. We believe that the importance of the research question with subsequent major implications to NHS service delivery merits this modest delay. The trial will not affect prompt delivery of PTNS or other NHS treatments to non-trial patients.

Early Termination of Study

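### The analysis section imputes every missing follow-up score from baseline or the interim diary, which contradicts the available-case rule for secondary endpoints

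*Protocol*

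**What the plan says.** Three places in the Protocol deal with missing outcomes.

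- **Plan of Statistical Analysis.** The section opens with binary, count, ordinal and continuous outcomes, and then states: "Given the stability of FI over a short period of time, where follow-up scores are missing, these will be imputed using the baseline scores", or the interim bowel diary if available. No endpoint is excluded. The reason given in the next sentence is that the primary outcome would stay stable if there were no intervention.
- **Design, pragmatic consideration 1.** For the primary endpoint, a missing 14-week diary is replaced by the interim diary. If that is missing too, the participant is a non-responder and takes the baseline frequency. For the other endpoints, after giving the expected 6% dropout, it says: "This level is acceptable to analyse secondary endpoints using available case analysis".
- **Clinical outcomes.** The interim diary is justified because "outcomes will be analysed using the last available data on those participants who do not complete the final 2 week bowel diary". The next sentence says that participants who withdraw before the final visit have no secondary outcome data for analysis.

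The interim diary covers one week during treatment. The regular outcome is a two-week diary after treatment. Table 2 schedules the CRF 3 questionnaires at Visits 2 and 14 only.

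**The concern.** For secondary endpoints, an analyst who follows the analysis section and one who follows the Design section would analyse different sets of people. Take a participant who has an interim diary but no final one. For percentage and numeric change in episodes, that person is dropped under one rule and filled under the other. Questionnaire scores have no interim value, so the analysis section could fill them only from baseline. Global impression of success is among the outcomes the section covers, but it is not on the list of baseline CRF 3 questionnaires, so there is nothing to carry forward.

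The stated rationale does not fit the people being filled in. Only participants who received a first treatment enter the analysis, so none of them is untreated. The sample-size section also expects substantial change in both arms: "we have selected a sham response rate of 35% whilst keeping this more conservative estimate of treatment response of 55"%. A baseline fill assumes zero change, and a single filled value enters the model as if it had been measured.

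For the primary endpoint the question is narrower: whether a one-week diary taken during treatment can stand in for a two-week diary taken afterwards.

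**Working it through.** **Inputs from the Protocol.** Responder rates 55% and 35%, 80% power, 5% significance, 212 participants with "106 in each arm", 6% dropout after the first treatment, and response defined as a reduction of at least 50%. Sidedness is not stated; two-sided is assumed.

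**1. The plan's own sample size.**
n = [1.96·√(2·0.45·0.55) + 0.8416·√(0.55·0.45 + 0.35·0.65)]² / 0.20² = (1.379 + 0.580)² / 0.04 = 95.9.
Continuity correction: (95.9/4)·[1 + √(1 + 4/(95.9·0.20))]² = 105.7, so 106 per arm and 212 in total. The stated figure reproduces, and nothing below changes it.

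**2. Secondary endpoints: the two rules compared.**
- Missing cases: 0.06 × 212 = 12.7, about 13.
- Available case: 0.94 × 212 = 199.3, about 199 analysed.
- Baseline fill: 212 analysed, with zero change in each filled case. If completers change by Δ on average, the reported mean change is 0.94·Δ + 0.06·0 = 0.94·Δ. The same factor applies to the difference between arms if dropout is equal.
- From the head count alone, the standard error is multiplied by √(199.3/212) = 0.97, about 3% too small. The documents give no standard deviations, so the rest of the effect on precision is not quantified.

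**3. Primary endpoint: do the sections agree?** Design orders the steps: interim diary, then baseline with non-responder status. The analysis section (baseline, or interim if available) and Clinical outcomes (last available data) lead to the same value. There is no conflict.

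**4. Primary endpoint: one-week against two-week diary.** The documents give no mean or dispersion for this purpose, so these are assumptions. Each participant's weekly rate λ is gamma with mean 4 and shape 1 or 2. The baseline count B is Poisson(2λ). The follow-up count F over w weeks, with true reduction r, is Poisson(wλ(1−r)). A participant is a responder if F ≤ wB/4. Zero baselines are excluded.

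| True reduction | One week | Two weeks |
|---|---|---|
| None | 23–26% | 16–19% |
| 50% | 58–60% | 57–59% |
| 70% | 78–80% | 82–83% |

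Sensitivity with no true change, two weeks against one:
- Plain Poisson: 37.0% v 42.9% (mean 1 per week), 22.5% v 30.6% (2), 15.6% v 23.9% (3), 8.4% v 15.8% (5), 2.2% v 6.5% (10). The one-week diary adds 4 to 8 points.
- With week-to-week over-dispersion (extra variance 0.5), it adds 8 to 9 points.

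Trial level: 0.06 × 7 points = 0.42, and 0.06 × 9 points = 0.54, so about 0.4 to 0.5 point per arm. This is an upper figure, because not every dropout will have an interim diary. It covers diary length only. The effect of measuring mid-treatment cannot be computed from the documents.

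**The case against.** The best defence is that the analysis section meant the primary outcome only. Its justification names that outcome, and Clinical outcomes already says that withdrawals have no secondary data. On that reading the fault is one sentence of loose scope. This is probably what happened, and it keeps the point modest. The rule as written still covers every follow-up score, and the same section commits to avoiding departures from the plan, so the scope has to be stated.

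A second defence is that the amount of missing data will be small. Missed interim and final diaries are to be attempted again, and anyone with an interim diary contributes data collected under treatment. That stands. Available-case analysis also has an assumption of its own, that dropout is unrelated to outcome given the model's covariates. The Design section allows that people may stop for lack of response, and if those people truly did not change, a zero-change fill would be right for them.

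A reader might go further and infer that the primary estimate depends on which section is followed, or that the 20-point effect could become 16.1 points (0.55×0.91 − 0.35×0.97) or 21.5 points (0.55×0.97 − 0.35×0.91). The documents do not support this. The sections agree on the primary endpoint. Those two figures score every dropout as a non-responder, skipping the interim-diary step that comes first. They also rest on a 9% v 3% split by arm, whereas the Protocol gives only 6% overall, and on dropouts otherwise responding at their arm's rate.

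**Conclusion.** The contradiction is real and confined to secondary endpoints. Following the analysis section instead of the Design section replaces about 199 observed cases with 212 partly filled ones. It shrinks a mean change to 0.94 of its size if all dropouts are filled from baseline and would otherwise have changed as completers did, and it makes standard errors about 3% too small from the count alone. The effect is small at 6% dropout and grows if dropout is higher or differs by arm. The stability rationale does not justify the fill for treated participants.

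The primary rule is consistent and can stay. Defining participants without data as non-responders is a composite outcome, so no imputation variance is lost there, and statisticians could reasonably differ on replacing the rule with multiple imputation. A reader might infer that the interim diary always inflates response. It does so with little or no true change (23–26% v 16–19% under the assumed gamma-Poisson model), makes almost no difference at a true 50% reduction, and slightly lowers response at 70%. At about 0.4 to 0.5 point per arm it calls for a sensitivity analysis, not a new primary rule.

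**What to change.** - In Plan of Statistical Analysis, limit the imputation sentence to the primary outcome. In Clinical outcomes, limit the last-available-data sentence in the same way. Leave the stepwise rule in Design as the single primary rule.
- State that secondary endpoints use available-case models adjusted for baseline, as Design already intends. Global impression of success is analysed without a baseline term if none is collected.
- Add one sensitivity analysis for the primary: multiply impute the 14-week diary count with baseline and interim diary as predictors, then derive responder status. Keep the imputation model small, since about 13 missing cases spread over at least 14 centres cannot support many terms.

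The cost is a change of wording and a little more analysis. No new data are needed, and 212 stands. The change should be made before unblinding, so that the choice of rule cannot follow the results.

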Appendix 1: Study Centre Codes

[figure not shown]
Aintree University Hospitals NHS Foundation Trust	ANT
Barts and the London NHS Trust	BLT
United Hospitals Bristol NHS Foundation Trust - Bristol Royal Infirmary	BRI
University Hospital of North Durham	CDD
Hull and East Yorkshire Hospitals NHS Trust - Castle Hill Hospital	CHH
Homerton University NHS Foundation Trust	HNT
South London Healthcare NHS Trust - Queen Elizabeth Hospital, Woolwich	QEH
Nottingham University Hospitals NHS Trust - Queen's Medical Centre	QMC
St Marks Hospital, Northwick Park	SMH
Salford Royal NHS Foundation Trust, Manchester	SRH
Sheffield Teaching Hospitals NHS Foundation Trust	STH
Sandwell and West Birmingham NHS Trust	SWB
University College London Hospitals	UCL
University Hospitals of Leicester - Leicester General Infirmary	LGI
University Hospital Southampton NHS Foundation Trust	SOT
Whipps Cross University Hospital, London	WCU
University Hospital of South Manchester, Wythenshawe Hospital	USM
University Lincolnshire Hospital Trust - Pilgrim Hospital	ULH
Glan Clywd Hospital, Rhyl	GCH
Guy's and St Thomas' Hospital NHS Trust	GST
Leeds Teaching Hospitals NHS Trust - Leeds Royal Infirmary	LRI
Mid Yorkshire Hospitals NHS Trust	MYH
Northern Lincolnshire & Goole Hospitals NHS Trust	NLG
Rotherham Hospital NHS Foundation Trust	RHT
The Royal Liverpool and Broadgreen University Hospitals NHS Trust	RLU
Taunton & Somerset NHS Trust	TST
Poole NHS Foundation Trust	PHT

CONtrol of Faecal Incontinence using **D**istal **N**euromodula**T**ion (CONFIDeNT)

Standardised PTNS and Sham

[figure not shown]
EQUIPMENT SET UP

Figure 1

- Just distal to calcaneus on sole of foot in midline (active for PTNS)
- 2. Bottom of foot just proximal to smallest toe
- 3. Top of foot just above smallest toe

Figure 2

PTNS: Urgent ® PC neuromodulation system (Uroplasty Ltd., Manchester, UK).

- Needle: Lower inner aspect of the RIGHT leg three finger breaths (5 cm) cephalad to the medial malleolus and approximately one fingerbreadth (2 cm) posterior to the tibia. 60-degree angle between electrode and ankle.
- Electrode: Ipsilateral calcaneus.

TENS: Biostim M7 TENS unit, Biomedical Life Systems, Vista, California

• Electrodes: Right foot, one under the little toe and one on top of the foot.

FOR PTNS:

- Set up both machines.
- Place tape over wire connected to PTNS needle (so appearance is identical to sham).
- Only turn on PTNS machine fixed-pulse frequency of 20Hz and a pulse width of 200 microseconds
- Continue treatment as usual increasing amplitude until a sensory or motor response reduce.
- DO NOT ALLOW PARTICIPANT TO ALTER SETTINGS THEMSELVES

FOR SHAM:

- Set up both machines. With PTNS, DO NOT CONNECT LEAD TO PTNS NEEDLE.
- Instead, tape lead near needle so it is not possible to tell at a glance if connected or not.
- Pick up both the TENS and PTNS machines
- Check TENS settings pulse frequency 10Hz and pulse width 200 microseconds.
- Press buttons simultaneously on PTNS and TENS machines to increase Amplitude (participant will only fell TENS as PTNS machine is not properly connected). THE PARTICIPANT WILL THEN HEAR THE BEEPS FROM THE PTNS MACHINE AS IN THE PTNS ARM.
- When a significant sensory of motor response is observed, turn down one setting.
- Press timer button twice 30 mins will count down on TENS display
- Leave the participant as usual for the 30 minute treatment.
- DO NOT ALLOW PARTICIPANT TO ALTER SETTINGS THEMSELVES

VERBAL EXPLANATION TO PARTICIPANT

"I am now going to start the nerve stimulation treatment. I will be inserting a small electrode needle, like an acupuncture needle, into your leg and putting sticky electrodes onto your foot. When I turn the machine you will be asked when you can first feel an electrical sensation in your ankle or foot. Occasionally you may also feel numbness or slight movement of your toes. This is normal. I will set the machine up and leave it running for 30 minutes. You may or may not continue to feel the stimulation during this time – this is normal also. After 30 minutes have elapsed I will remove the needle and sticky electrodes (the machine automatically turns off at this time). If the treatment becomes uncomfortable at any point please let me know and I will turn it down or stop the machine."

References

- 1. Nelson RL. Epidemiology of fecal incontinence. Gastroenterology 2004; 126 (suppl 1):S3-S7.

subsequent a	amendm	nents will be	e conducte	ed in acc	ordano	ce with the Re	11, dated 16 th esearch Govern	nance F	ramework for
		, , ,					aration of Hels amendments	,	,

PROTOCOL DOCUMENT

CONtrol of Faecal Incontinence using **D**istal **N**euromodula**T**ion (CONFIDeNT)

The clinical study as detailed within this research protocol (Version 11, dated 16th July 2012) , or a subsequent amendments will be conducted in accordance with the Research Governance Framework the Health & Social Care (2005), the World Medical Association Declaration of Helsinki (1996) and the social care (2005).	o
current applicable regulatory requirements and any subsequent amendments of the appropria regulations.	
Principal Investigator Name:	
Principal Investigator Site:	
Signature and Date:	

Addendum to Protocol: Inclusion of 1 year follow-up study.

Rationale

The aim of the CONFIDeNT Study is to ascertain efficacy of PTNS vs sham stimulation in patients with faecal incontinence. This study is pivotal in developing the most effective treatment protocol for patients with FI. It does not however examine the long-term effectiveness of PTNS, which could be easily ascertained with a further observational follow-up study. Upon completion of the CONFIDeNT Study, following up both PTNS and sham patients for 1 year would provide useful data regarding 'disease-free survival', requirement and timing of top-up treatments, effects on quality of life, acceptability of PTNS and health economic analysis.

Aims

This 1-year observational study will follow up all CONFIDeNT Trial participants to inform about long-term effectiveness of PTNS treatment and requirement for 'top-up' treatments. It will also inform regarding the outcome of sham patients. All participants would be contacted at 6 months and 1 year after their final PTNS or sham treatment. Further, participants who had successful PTNS treatment will contact their CONFIDeNT centre if and when they perceive loss of efficacy, and time to this loss of efficacy will be documented.

Design

All participants who completed the CONFIDeNT Trial will be followed up by the lead centre, Queen Mary University London, at 6 months and 1 year following PTNS or sham treatment by post/email and telephone. Follow up will consist of questionnaire data and bowel diaries.

The bowel diary will be that used in the CONFIDeNT Study. The questionnaire is entitled the 'CONFIDeNT Study follow-up Questionnaire, and includes the Cleveland Clinic Faecal Incontinence Score and the EQ-5D questionnaire.

In addition, patients will be able to contact their local centre in the intervening time if they perceive loss of efficacy of successful PTNS or sham treatment. At this time, length of efficacy of treatment will be recorded for each patient. Patients are free to have further 'top-up' PTNS sessions or any other treatment for FI during this study.

Eligible participants

All participants who complete the CONFIDeNT Trial will be eligible for inclusion into the follow-up study.

46

Events

Visit 13 CONFIDeNT Study: Participants will be invited be involved in the follow-up study and given a Participant Information Sheet at this visit if interested.

Visit 14 CONFIDeNT Study: At Visit 14, two weeks later, a member of the local team (trained in informed consent) will answer any outstanding questions and thence ask participants to sign the study consent form. The local study team member will then re-confirm the participants contact details, and register the participant on the enrolment log for the follow-up study. Each participant will give consent for his or her contact details to be securely passed on to the lead centre where the follow-up study will be co-ordinated.

After CONFIDeNT Study Visit 14: Contact details of those participants enrolled on the follow-up study will be passed on to the lead centre in the same way as for the CONFIDeNT Study as detailed above 'All trial data will be collected from each participating site either in person by the Academic Clinical Fellow in a locked bag, or sent by special courier, and transported back to the Lead Centre, Barts and the London NHS Trust'.

6-months following CONFIDeNT Study completion: Participants will be contacted by telephone to confirm that 6 months have passed since completion of the study. They will be asked how they wish to complete the follow-up questionnaires; either by telephone interview with the Academic Clinical Fellow, via email or by post. Questionnaires and a 2 week bowel diary will be completed appropriately and collated at the Lead Centre.

12-months following CONFIDeNT Study completion: Participants will be again contacted by telephone to confirm that 1 year has passed since completion of the study. They will be asked how they wish to complete the follow-up questionnaires; either by telephone interview with the Academic Clinical Fellow, via email or by post. Questionnaires and a 2 week bowel diary will be completed appropriately and collated at the Lead Centre. Involvement in the study will then cease.

At any time following enrolment in Follow-up Study: Patients who perceive a deterioration in the efficacy of successful PTNS will contact their local study centre for follow-up. The time to this deterioration will be documented in each study centre.

Loss to follow-up

Three attempts will be made to contact each participant at 6-months and 1-year by telephone and post/email. If these are unsuccessful, the patients will be presumed lost to follow-up.

Withdrawal from study

If participants wish to withdraw from this follow-up study, they will be free to do so at any time without giving a reason.

Trial outcomes

The pragmatic primary outcome of this 1 year observational follow-up study is continued efficacy i.e. a binary outcome of whether PTNS (or sham) has continued perceived efficacy by the patient, or not.

The following secondary outcomes will be studied:

- 1. Requirement and timing of PTNS 'top-up' treatments
- 2. Requirement for other treatments or surgery for FI
- 3. Acceptability of PTNS treatment
- 4. Effect on FI measures and quality of life
- 5. Formal assessment of health utilisation

Plan of statistical analysis

The primary outcome will take the form of binary category (on-going success or failure of treatment) vs. time. Secondary outcomes include counts (change in number of FI episodes), ordinal (patient's global impression of success) and continuous (Wexner score, EQ-5D) data. Appropriate analytical methods will be used to compare PTNS to sham and gain a measure of disease-free post-treatment survival (time series, censored for loss of follow up) and cost effectiveness over time (using EQ-5D).

Analysis will be performed using proprietary software (Stata version 10.1, Stata Corp. Texas) by the study statistician. P < 0.05 will be taken to indicate statistical significance.

Project timetable

We propose a total study duration of 24 months. Our proposed study milestones will be:

September 2012: Recruit first patient to CONFIDeNT follow up study

August 2013: Last patient recruited to CONFIDeNT Study
October 2013: Last patient recruited to follow-up study

October 2014: Last follow up from CONFIDeNT follow up study.

Funding

Full funding has been secured for this study from Uroplasty Ltd.
